5.1.3 Concomitant medication date imputation

Please refer to [Section 5.1.2](#).

5.1.4 Prior therapies date imputation

Consider specific imputation rules for partial dates.

Start date:

The same rule which is applied to the imputation of AE/concomitant medication ([Section 5.1.2](#)) start date will be used with the exception that scenario (B) will be replaced to be 'start date of study treatment - 1'.

End Date:

Imputed date = min (start date of study treatment, last day of the month), if day is missing;

Imputed date = min (start date of study treatment, 31DEC), if month and day are missing.

If the end date is not missing and the imputed start date is after the end date, use the end date as the imputed start date.

If both the start date and the end date are imputed and if the imputed start date is after the imputed end date, use the imputed end date as the imputation for the start date.

5.1.5 Post therapies date imputation

If the day of the medication date is missing the following imputation rules will be followed:

- If the treatment end month and year and medication month and year are the same, then the day of the medication date is set to treatment end day + 1.
- If the month or year of the medication date is after the treatment end month/year then the day of the medication date set to the first of the month.

If the month of the medication date is missing the following imputation rules will be followed:

- If day is also missing,

- If the treatment end year and medication year are the same, then the month of the medication date is set to treatment end date + 1.
- If the year of the medication date is after the treatment end year then the month of medication date set to be 01-JAN.
- If day is not missing,
 - If the treatment end year and medication year are the same and if medication day is before the day of treatment end date, then the month of medication date is set to month of treatment end date + 1.
 - If the treatment end year and medication year are the same and if medication day is after the day of treatment end date, then the month of medication date is set to month of treatment end date.
 - If the year of the medication date is after the treatment end year then medication date set to be JAN.

If the year of the medication date is missing there is no imputation.

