7.1.5 Follow-up period

Safety Follow-up

All patients must have safety evaluations until 150 days after the last dose of PDR001 or 90 days after the last dose of MCS110 (whichever the longer). The 30-, 90- and 150-day safety follow-up can be done by telephone call or visit.

Concomitant medications will be collected until the 30-day safety follow-up has been completed or the start of a new antineoplastic therapy, whichever occurs first.

Data collected should be added to the Adverse Events CRF, the antineoplastic therapies since discontinuation of study treatment CRF, and the Concomitant Medications CRF.

For a female participant of child bearing potential, a pregnancy test will be performed on a monthly basis after stopping the study treatment ([Section 7.2.2.5.7](#)).

For patients who transfer to another clinical study to continue provision of study treatment or an alternative treatment option, as described in [Section 4.3](#), the follow-up for safety will not be performed. For all other patients, the safety evaluation period will be completed but the disease-progression and survival follow up will not be performed.

Disease progression follow-up period

Patients who discontinue study treatment for any reason other than death, disease progression per irRC, lost to follow-up, consent withdrawal, start of new cancer therapy or study

termination, should return for tumor evaluation assessments every 9 weeks until 51 weeks, then every 12 weeks until progression of disease per irRC, withdrawal of consent, lost to follow-up ([Section 7.2.1](#)), or until the end of the study is reached as described in [Section 4.3](#).

If patients refuse to return for these visits or are unable to do so, every effort should be made to contact them or a knowledgeable informant by telephone to determine if the patient had disease progression.

For patients who transfer to another clinical study or an alternative treatment option to continue provision of study treatment, the follow-up for disease progression will not be performed.

Survival follow-up period

Upon completion of the safety follow-up and disease progression follow-up (if applicable), all patients enrolled in the Phase Ib and Phase II parts will be followed for survival every 3 months (can be done by telephone call) until death or until the end of the study is reached, as described in [Section 4.3](#), unless they withdraw consent or are lost to follow-up.

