2.7.3 Handling of missing values/censoring/discontinuations

Patients in the phase II part who have BOR of unknown (UNK) or not assessed (NA) will be considered as a treatment failure in the secondary analysis of ORR according to irRC.

For the analysis of PFS, patients without documented disease progression or death are censored at the time of last valid tumor assessment documenting non-progression (one of complete response, partial response, or stable disease). Patients without any valid post-baseline tumor assessment response (one of CR, PR, SD, or PD) will be censored on the start date of treatment. Patients who have a PFS event (progression or death) after two or more consecutive missing assessments from the last valid tumor assessment will be censored on the last valid tumor assessment (or on the start date of treatment among those with only one valid postbaseline tumor assessment).

Other missing data will simply be noted as missing on appropriate tables/listing.

If any alternative cancer therapy is taken while on study any subsequent efficacy assessments would be excluded from all relevant efficacy summary.

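### SAP 5.1.5 dates a partial new-therapy start at the earliest allowed day without checking documented progression, so a PD found after treatment end can be dropped and PFS censored before it

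*SAP*

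**What the plan says.** SAP 5.1.5 has a rule for each kind of partial date of a therapy taken after study treatment:

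- Day missing, same month as treatment end: "then the day of the medication date is set to treatment end day + 1".
- Day missing, later month: "then the day of the medication date set to the first of the month".
- Day and month missing, same year as treatment end: "then the month of the medication date is set to treatment end date + 1".
- Day and month missing, later year: "If the year of the medication date is after the treatment end year then the month of medication date set to be 01-JAN".

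None of these refers to a progression date or a scan. Section 5.1.5 does not say whether treatment end is the last administration, the last date of exposure or the end-of-treatment (EOT) visit.

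SAP 2.7.3 states: "If any alternative cancer therapy is taken while on study any subsequent efficacy assessments would be excluded from all relevant efficacy summary". SAP 2.1.1 and 2.5.3 say the same. For PFS, "patients without documented disease progression or death are censored at the time of last valid tumor assessment documenting non-progression", and patients with no valid post-baseline assessment "will be censored on the start date of treatment".

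Protocol Appendix 1 lists new anti-cancer therapy among the PFS censoring reasons (14.1.4.5.6). Its default is to censor at the last adequate assessment (Table 14-5, Situation F, option 1).

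**The concern.** Each branch picks the earliest day consistent with what was recorded. If a PD scan lies between the imputed and the true start, the analysis treats the therapy as having come first, discards the PD and censors the patient at an earlier scan. The patients exposed are those whose disease progressed and who then moved to another treatment, so the censoring is informative and tends to raise the Kaplan-Meier PFS curve. DOR is exposed in the same way, because Appendix 1 gives it the time-to-progression end date and censoring.

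The imputed order is also the less plausible one. Protocol 7.1.5 lists "consent withdrawal, start of new cancer therapy" among the reasons for which patients are not asked to return for progression scans, and 6.4.2 prohibits other anticancer therapy during the study. SAP 5.1.4 does check chronology for prior therapies (an imputed start may not fall after the end date). Section 5.1.5 has no such check, although its date can remove efficacy data.

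**Working it through.** The plan gives no figure to reproduce here, so the check applies the written rules to dates.

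**Condition for loss.** Let E be treatment end, P the first PD, T the true therapy start and I the imputed start. PD is excluded when I < P. Every branch gives I of at least E + 1, so a PD on or before E is never lost. Over all treatment-end dates in 2018 and true starts 1 to 399 days later, I was never later than T. The largest shortfall was 30 days with the day missing and 364 days with day and month missing.

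**Day missing.** Suppose E is at least two days before P. If T is in the month of E, then I = E + 1 < P. If T is in a later month, I is the 1st, which precedes P only when P is in the same month as T and is not itself the 1st. With a gap of g days from P to T, a month of L days therefore contributes max(0, L − g − 1) losing PD dates. Over a 365-day year:

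| Gap g (days) | Losing PD dates | Share of 365 |
|---|---|---|
| 7 | 365 − 12×8 = 269 | 73.7% |
| 14 | 365 − 12×15 = 185 | 50.7% |
| 21 | 365 − 12×22 = 101 | 27.7% |
| 28 | 365 − 12×29 + 1 = 18 | 4.9% |

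(The + 1 in the last row is because February contributes 0 rather than −1.)

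**Day and month missing, T in the year of E.** I = E + 1 < P, so PD is lost in 100%.

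**Meaning of treatment end.** The counts hold under any reading that puts E at least two days before P.

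- Last administration (SAP 2.1.1): a PD at the next Day 1, 21 days after the last dose, is exposed.
- Last administration + 20 days (last exposure, SAP 2.4.1): with PD at exactly 21 days, E + 1 = P, so nothing is lost.
- EOT visit (Protocol 7.1.3; Appendix 1, 14.1.3.2.7): no loss if the visit is on the PD date.
- PD 28, 35 or 63 days after the last dose: the table and the 100% apply under last dose, last dose + 20, and an EOT visit 14 days after the last dose.

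**Worked patients.** First dose 8 January 2018, dosing every 3 weeks, scheduled scans 19 February, 2 April and 14 May. Treatment end is read as last dose; PFS day = date − 8 January + 1.

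| | Last dose | Previous non-PD scan | PD | New therapy (as recorded) | Imputed | Correct PFS | PFS under the SAP |
|---|---|---|---|---|---|---|---|
| A | 23 Apr | 19 Feb | 2 Apr | 28 May (May) | 1 May | event, day 85 | event, day 85 |
| B | 23 Apr | 2 Apr | 14 May | 28 May (May) | 1 May | event, day 127 | censored, day 85 |
| C | 12 Mar | 19 Feb | 26 Mar | 30 Mar (March) | 13 Mar | event, day 78 | censored, day 43 |
| D | 29 Jan | none | 19 Feb | 26 Feb (February) | 1 Feb | event, day 43 | censored, day 1 |
| E | 12 Mar | 19 Feb | 14 May | 10 Sep (year only) | 13 Mar | event, day 127 | censored, day 43 |
| F | 23 Apr | 2 Apr | 14 May | 10 Jun (June) | 1 Jun | event, day 127 | event, day 127 |

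Patient E, whose PD comes 63 days after the last dose, is lost under the other readings too. Treatment end on 1 April (last dose + 20) gives 2 April, and an EOT visit on 26 March gives 27 March; both precede 14 May.

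**The case against.** The strongest case on the other side has five parts.

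1. *Treatment end is undefined, and the loss at the next Day 1 depends on it.* This stands for a PD exactly 21 days after the last dose, which is safe under two of the three readings. It does not protect a PD found later in follow-up.
2. *Many first PDs will precede the last dose.* Patients are not to stop for RECIST PD, and irPD needs confirmation after at least 4 weeks. This stands, and such RECIST PFS times are untouched.
3. *The link from 5.1.5 to PFS is inferred.* SAP 2.4.3 only lists later therapies, and the PFS paragraph of 2.7.3 does not name them as a censoring reason. This also stands. But the general exclusion sentence and Table 14-5 point the same way, and no document gives another rule for partial dates.
4. *Early dating guards against crediting results obtained under another drug.* That is a fair aim, and it argues against moving the date past every recorded scan. It does not justify discarding a documented first PD.
5. *The stakes are low.* PFS is secondary and descriptive, no success criterion uses it, and Protocol 9.4 provides for querying missing values. This limits the importance of the point but does not remove the defect.

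A reader might also infer that a recorded scan proves the new therapy had not begun. The documents do not support that. Protocol 7.1.5 says who should return for scans; it does not bar scans after new therapy, and the exclusion sentence presupposes that some occur.

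**Conclusion.** The point holds as a possibility created by a stated rule. When the new-therapy date is partial and the first PD is dated after treatment end, between the imputed and the true start, the PD can be excluded and PFS and DOR censored at the previous scan (PFS at day 1 for a first-scan PD). The percentages describe records that already meet those conditions; they are not rates among patients. They assume a 365-day calendar, PD dates spread evenly over it, the stated gaps, and treatment end at least two days before PD.

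A reader might multiply them by a guessed share of partial dates to obtain a percentage of patients affected. The documents give neither that share nor the share of patients whose first PD follows treatment end, so no such percentage is supported, and the effect on median PFS cannot be computed. Nor do they support saying that progression is routinely lost.

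Primary ORR is unaffected, since dropping a PD creates no CR or PR. The primary CBR of Group 2 was not part of this check. With about 20 patients per Phase II group, a few misclassified events could still show in a Kaplan-Meier curve, which makes an inexpensive correction worthwhile.

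**What to change.** Amend SAP 5.1.5 in two respects:

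- Define treatment end as one named date.
- Add: when the first documented PD falls within the period that the recorded month or year allows, the imputed start used for efficacy censoring is no earlier than that PD date + 1 day, capped at the end of the recorded month or year.

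Refer to this date in SAP 2.1.1, 2.5.3 and 2.7.3. Apply it separately for RECIST v1.1 and irRC PD. For irRC, say whether the first or the confirming scan dates the PD. Do not anchor to the last recorded tumor assessment: with only a year recorded, that could keep scans taken well into another therapy.

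In the worked patients, B, C, D and E return to events on days 127, 78, 43 and 127, while A and F do not change.

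The cost is the treatment-end definition, one added sentence with cross-references, and a small programming change; recorded data are not altered. The small downside is that a therapy truly started before the PD scan would be dated late, so that PD would count as an event.

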5.1.6 Other imputations

For partially missing date of first recurrence/progression, date of initial diagnosis or date of most recent relapse/progression the following imputation rules will be applied:

- If Month and Day missing, set to 01-Jul of the year
- If Day missing, set to 15 of the month

5.2 Laboratory parameters derivations

CTC grading for blood differentials is based on absolute values. However, this data may not be reported as absolute counts but rather as percentage of WBC.

If laboratory values are provided as '<X' (i.e. below limit of detection) or '>X', prior to conversion of laboratory values to SI unit, these numeric values are set to X.

The following rules will be applied to derive the WBC differential counts when only percentages are available for a xxx differential

$$\text{xxx count} = (\text{WBC count}) * (\text{xxx \%value} / 100)$$

Further derivation of laboratory parameters might be required for CTC AE grading. For instance, corrected calcium can be derived using the reported total calcium value and albumin at the same assessment using the following formula:

$$\text{Corrected Calcium (mg/dL)} = \text{Calcium (mg/dL)} - 0.8 [\text{Albumin (g/dL)} - 4]$$

In order to apply the above formula, albumin values in g/L will be converted to g/dL by multiplying by 0.1, calcium values in mmol/L will be converted to mg/dL by dividing by 0.2495. For calculation of laboratory CTC grades 0 and 1, the normal range for derived corrected calcium is set to the same limits (in mg/dL) as for calcium.

CTC grades for the derived absolute WBC differential counts (neutrophils, lymphocytes) and corrected calcium as defined in the previous section.

5.3 Rule of exclusion criteria of analysis sets

Patients will be excluded from the analysis sets based on the protocol deviations entered in the database and specific non-protocol deviations. All protocol deviations and non-protocol deviations leading to exclusion from specific analysis sets will be finalized before database lock.

Table 5-3 displays non-protocol deviations leading to exclusion from analysis set definitions. These table will be updated before database lock.

Table 5-3 Non-protocol deviations leading to exclusion from analysis set definitions

Summary of non PD	Analysis set(s) to be excluded
No post-baseline safety assessment	SS
1. Patient, who has not experienced DLT, was not observed for ≥ 42 days following the first dose or had not completed the required safety evaluations for Cycle 1 and Cycle 2 or 2. Patient who has not experienced DLT, didn't receive two doses in the first two cycles.	DDS
Patient did not have at least one primary PK parameter	PAS

6 Reference

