10.1.2 Safety Set

The Safety Set (SS) includes all patients who have received at least one dose of MCS110 or PDR001. Patients will be classified according to treatment received, where treatment received is defined as:

1. The treatment assigned if it was received at least once, or
2. The first treatment received when starting therapy with study treatment if the assigned treatment was never received.

The safety set will be used for the safety summary of the study.

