2.2.2 Safety Set

The safety set (SS) includes all patients who have received at least one dose of MCS110 or PDR001. Patients will be classified according to treatment received, where treatment received is defined as:

1. The treatment assigned if it was received at least once, or
2. The first treatment received when starting therapy with study treatment if the assigned treatment was never received.

The safety set will be used for the safety summary of the study.

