2.4 Treatments (study treatment, rescue medication, concomitant therapies, compliance)

The Safety Set will be used for all medication data summaries and listings.

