2.8 Safety analyses

The assessment of safety is based on the type and frequency of Adverse Events (AEs) as well as on the number of laboratory values that fall outside of pre-determined ranges (Common Toxicity Criteria for Adverse Events (CTCAE) grading limits or normal ranges as appropriate). Other safety data include electrocardiogram and vital signs.

The safety set will be used for summaries and listings of safety data with the exception of DLTs for which the DDS will be used.

The overall observation period will be divided into three mutually exclusive segments:

1. pre-treatment period: from day of patient's informed consent to the day before first dose of study treatment
2. on-treatment period: from day of first dose of study medication to 30 days after the last dose of study treatment
3. post-treatment period: from 31 days after date of last administration of study treatment

Safety summaries will primarily be based on all data from the on-treatment period. Following last administration of study treatment, adverse events (including serious adverse events), and new antineoplastic therapies are collected for a period of 150 days for PDR001 and 90 days for MCS110. Following start of new antineoplastic therapy, only treatment related adverse events will be collected. Select summaries of related adverse events will be produced for the combined on-treatment and post-treatment periods for patients receiving PDR001 (see [Section 2.8.1](#)).

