2.8.2 Deaths

All deaths occurred in the study will be listed with principal cause reported/preferred term and following summaries will be produced:

- All deaths with cause of death by primary system organ class and preferred term

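### SAP Table 5-3 excludes from the Safety Set on a condition that the set's own definition lacks, and so can remove treated patients from the safety tables

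*SAP*

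**What the plan says.** SAP 2.2.2 gives one entry condition: "The safety set (SS) includes all patients who have received at least one dose of MCS110 or PDR001". Protocol 10.1.2 gives the same one: "The Safety Set (SS) includes all patients who have received at least one dose of MCS110 or PDR001". Neither asks for any assessment after dosing. The rest of each section only says under which treatment a patient is classified.

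SAP 5.3 then gives exclusion rules. It introduces its table as operative: "Table 5-3 displays non-protocol deviations leading to exclusion from analysis set definitions". The first row reads "No post-baseline safety assessment" and names the Safety Set as the set affected. The section adds "These table will be updated before database lock".

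The set matters because of where it is used. SAP 2.8 says "The safety set will be used for summaries and listings of safety data", with dose-limiting toxicities (DLTs) as the only exception. SAP 2.4 says "The Safety Set will be used for all medication data summaries and listings", which covers exposure and dose intensity.

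**The concern.** A dosed patient with no later safety assessment is in the Safety Set under SAP 2.2.2 and out of it under Table 5-3. A programmer cannot follow both.

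Such an exclusion may also be related to outcome. Patients with nothing recorded after the first dose are mainly those who died, withdrew or were lost very early. Removing them changes the denominators of the safety tables, and the numerators too if they had events. In Phase Ib, safety and tolerability are the primary objective, and results are reported by dose level, some with only six patients. The efficacy rule in SAP 2.5.3 goes the other way: Phase II patients with unknown or unassessed response stay in the response-rate analysis as failures.

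**Working it through.** **1. The denominator under the definition.** The inputs are the study-status paragraphs of the protocol's Amendments 04 and 05.

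- Phase Ib dose levels: 6 + 12 + 12 + 13 + 6 + 11 = 60.
- Phase II groups: 20 + 20 + 21 + 20 = 81.
- Total: 60 + 81 = 141, which matches the protocol's stated number treated.

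The Full Analysis Set (SAP 2.2.1) has the same dose-only condition, so by definition the two sets have the same members. With the Table 5-3 row applied, the Safety Set has 141 − k patients, where k is not given.

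**2. Is the row only a restatement?** Compare the rows of Table 5-3 with the definitions in SAP 2.2.

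| Set | Condition in SAP 2.2 | Row in Table 5-3 |
|---|---|---|
| Dose-determining set (DDS) | DLT, or two doses plus at least 42 days of observation and sufficient safety evaluation | Restates this |
| Pharmacokinetic set | At least one primary PK parameter (with planned treatment) | Restates this |
| Safety Set | At least one dose | Adds a post-baseline assessment |

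Only the Safety Set row brings in something new.

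**3. Is it a declared change?** For the analysis sets, SAP section 4 records that per-protocol outputs were not produced and that a consent-withdrawal section was added. For the exclusion rules, it records that the protocol-deviation table was removed. It declares no new condition for the Safety Set.

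**4. Who could meet the row?** The term is undefined, and two readings are possible.

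- *Broad:* any post-dose ECG or adverse-event record counts. Protocol Table 7-5 schedules an ECG one hour after the last infusion on Cycle 1 Day 1, and Table 7-1 shows continuous adverse-event collection. Few or no patients would be excluded.
- *Narrow:* a later visit or laboratory sample is needed. In Table 7-1 the next of these is Cycle 1 Day 8, so first-week deaths and losses would be excluded.

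No document chooses between them.

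**5. Hypothetical size.** Suppose x of n patients have an event, and k are excluded, of whom j had the event. The rate x/n becomes (x − j)/(n − k). The values of x, k and j below are assumptions.

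| Setting | Definition | k = 1, excluded patient had the event | k = 1, excluded patient did not |
|---|---|---|---|
| Phase II group, x = 4 | 4/20 = 20.0% | 3/19 = 15.8% | 4/19 = 21.1% |
| Six-patient dose level, x = 1 | 1/6 = 16.7% | 0/5 = 0% | 1/5 = 20.0% |
| All treated, x = 1 | 1/141 = 0.7% | 0/140 = 0% | 1/140 = 0.7% |

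With k = 0 nothing changes. The shift can go either way, and it is largest where groups are smallest.

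**The case against.** The strongest reply accepts the textual conflict and disputes the consequences.

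- **The row may catch nobody.** On the broad reading, a patient with a post-dose ECG or a reported event has been assessed. Serious adverse events must be reported within 24 hours (Protocol 8.2.2), so a patient with a recorded early fatal event would probably stay in. The patients excluded would then be those without recorded events, and rates would rise. This stands, and it is why the arithmetic is shown in both directions.
- **Early deaths would still appear elsewhere.** A reader might infer that the row hides early deaths from the report. The documents do not support that. Disposition uses the Full Analysis Set (SAP 2.3.1), survival is listed for all enrolled patients (SAP 2.7.2), and SAP 2.8.2 says "All deaths occurred in the study will be listed with principal cause reported/preferred term". What could change is whether such a patient counts in tables based on the Safety Set. Some tension remains, because SAP 2.8 bases safety listings on that set.
- **DLT reporting is hardly touched.** Since the DDS is drawn from the Safety Set, a reader might infer that an early DLT could be lost. But a DLT is itself an adverse event or abnormal laboratory value (Protocol 6.2.4), so on the ordinary reading that patient has post-baseline safety data. A patient with neither a DLT nor assessments already fails the DDS conditions. That inference does not hold.
- **The table is provisional.** It is due for update before database lock. That gives an occasion to correct the row but does not commit the sponsor to doing so.

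**Conclusion.** The inconsistency is certain. Table 5-3 imposes a condition on the Safety Set that Protocol 10.1.2 and SAP 2.2.2 do not contain and that SAP section 4 does not declare. Its effect on results is unknown and may be nil, because the number of dosed patients without a post-baseline safety assessment is not reported and the term is undefined.

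The supportable statement is that the row can remove early deaths, withdrawals and losses from the safety and exposure tables. The documents do not show that it will. The percentages illustrate one excluded patient and do not estimate what happened. The point should still be settled before database lock: the exclusion may depend on outcome, and in Phase Ib it bears on the population for the primary objective.

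**What to change.** Delete the Safety Set row from Table 5-3, or replace it with one that excludes only patients who received no dose of either study drug. State that dosed patients without post-baseline data stay in the denominators, with missing values shown as missing. The Safety Set then has the same members as the Full Analysis Set: 141 treated patients, 60 in Phase Ib and 81 in Phase II.

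The cost is one table row and one sentence in the SAP. No new data are needed, and if no patient meets the row, no result changes.
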